## Methodology

### Study design

This study will employ a randomized, single-blinded, two-group, repeated measure design (Table 1).

Table 1. *Experimental design of the internal pilot study*

Group/Week			Week 1	Week 2-7	Week 8	Week 9-14	Week 15
M	R	A	O1	Orthosis	O2	Orthosis+OTTO	O3
M	R	B	O1	No treatment	O2	OTTO	O3

*Note.* M = matching with severity of motor function of the upper extremity; R = random assignment; O1,2,3 = time points for outcomes measures; Orthosis = six weeks of forearm rotation-assist orthotic intervention; OTTO = six weeks of OT task-oriented approach intervention.

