### Study endpoints

The primary endpoint is the functional improvement. “Functional improvement” represents improvement in the performance of everyday activities. The secondary endpoints are active range of motion and muscle strength, including grip and pinch, of the involved upper extremity as well as orthosis compliance.

Outcome measures for the primary endpoint include the *Canadian Occupational Performance Measure* (COPM) for self-perceived functional performance and satisfaction with performance, the *Wolf Motor Function Test* (WMFT) for quantitatively measuring the motor function of the upper extremity, and the *Motor Activity Log* (MAL) for measuring participants’ actual use of the involved arm in the real world.

Outcome measures used for the secondary endpoints include goniometric measurements for active and passive range of motion (ROM), hand-held dynamometry and manual muscle testing for muscle strength of the upper extremity, Jamar Dynamometer for grip strength, pinch gauge for pinch strength, as well as information collected by the Nike+ FuelBand regarding numbers of hours they wear the orthosis everyday throughout the study period for adherence with the orthosis.

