### **Treatment allocation**

Participants who are eligible and willing to participate in this study will first be matched with the severity of the motor function of the involved upper extremity measured by the upper extremity subscale of the Short Form Fugl-Meyer Motor Function Assessment. Participants will be classified as mild, moderate, and severe groups. Participants in each group will then be randomized in a 1:1 allocation ratio to either the Group A or B (Figure 1). The primary investigator, [name], will randomly assign eligible participants at the screening session using sealed envelopes with an equal number of both intervention

conditions to balance group size (10 for each matched group with 5 Group As and 5 Group Bs).

[figure not shown]

Figure 1. Study schematic for treatment allocation.

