**Data collection plan and schedule.** The timing of screening, randomization, and follow-up visits are illustrated in Figure 2. The primary investigator will screen potential participants' eligibility using the Mini-Mental Status Examination (MMSE), the Short Form Fugl-Meyer (S-FM), and ROM. There will be three time points for data collection (pretest, posttest 1, and posttest 2). Trained occupational therapy students recruited from the University of Minnesota and University of Puget Sound will serve as the blinded evaluators to implement all assessments except the COPM for each research site. The primary investigator will administer the COPM to obtain information that will be used to guide future interventions.

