## **Evaluation**

### **Data analysis**

The *R* software will be used for data analyses. Descriptive statistics will be used to analyze the demographic data, baseline information, and adherence with orthosis wearing. The linear mixed-effects model regression will be used as the omnibus test for examination of effect of intervention involving orthosis across time in comparison of that without. The

Orthosis for stroke  
Protocol Number: 1309M42881

systematic or fixed effects of this study are group assignment and time. Main effect of the two factors and the interaction effect between the two will be explored. Study participants will be considered and added into the model as the random effects.

General linear regression model will be used to determine effects of experimental conditions between the two groups. Data obtained from the pretest will first be used to examine if there are differences in outcome measures between the two groups. It will also serve as a covariate while examining difference between the two groups at the posttest 1. Data from the posttest 1 will serve as a covariate while examining difference between the two groups at the posttest 2. The *paired t* test will be used to examine difference within each group for each intervention period across time.

Interim monitoring of the data will occur after 16 participants complete the study. If the study results indicate a significant decline in functional performance for either group across the 12-week study, the study will be terminated. If there are serious adverse effects, the study would be terminated.

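### The unblinded primary investigator appears to draw the group at screening, before the baseline COPM, from envelope stacks fixed at 5 A and 5 B; assignment should follow completion of O1

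*Combined protocol and SAP*

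**What the plan says.** **Who assigns, when and from what.** Treatment allocation says that the primary investigator "will randomly assign eligible participants at the screening session using sealed envelopes with an equal number of both intervention". The rest of that sentence fixes the make-up of every stack: "conditions to balance group size (10 for each matched group with 5 Group As and 5 Group Bs"). The three severity groups are mild, moderate and severe. In the available text the envelopes are called sealed. It does not call them opaque or numbered, and it names no independent person to prepare or hold them.

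**Order of assignment and baseline.** Table 1 (Study design) lists M, then R, then the group, then O1 in week 1; its note reads "R = random assignment; O1,2,3 = time points for outcomes measures". The data collection paragraph of the Study plan adds: "The timing of screening, randomization, and follow-up visits are illustrated in Figure 2". That figure is not shown.

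**Who screens, treats and assesses.** "The primary investigator will screen potential participants", using among other tools the Short Form Fugl-Meyer, whose upper-extremity subscale sets the severity group. On the COPM: "The primary investigator will administer the COPM to obtain information that will be used to guide future interventions". The Study plan and Treatment Fidelity sections both leave the COPM out of the blinded evaluators' work, whereas the Data monitor section gives the blinded assessor every evaluation. Treatment Fidelity has the same investigator treat most participants. The document uses two titles for this person; I read them as one role.

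**How the baseline is used.** The Study endpoints section begins its list "Outcome measures for the primary endpoint include the" and names the COPM, WMFT and MAL. Of the pretest data, Data analysis says: "It will also serve as a covariate while examining difference between the two groups at the posttest 1". The pretest also enters the mixed model across time and the paired t test for the first period. The posttest 2 regression adjusts for posttest 1 instead.

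**The concern.** Two separate weaknesses come from one arrangement.

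1. **Baseline COPM with the group known.** Randomisation protects a baseline only if it is measured before the group is known. If the envelope is opened at screening and O1 follows, the COPM interviewer knows the group for every participant at baseline. That score is then treated as a pre-treatment covariate and as the starting point for change.

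2. **Partly predictable draws.** The person who draws each envelope knows all earlier draws, and the composition of each stack is fixed. Some eligibility criteria need judgement, such as sufficient cognition and adequate trunk and leg function. The available text gives no Fugl-Meyer cut-points for the three severity groups. Someone who can often guess the next arm therefore has room to influence who enters, or into which stack, without meaning to.

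The plan intends this study to supply effect sizes for a future study, so a distortion in the COPM comparison could carry into that study's planning.

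**Working it through.** **The plan's own figure.** 3 severity groups × 10 envelopes = 30, the planned enrolment, with 3 × 5 = 15 per arm. The envelope stock and the enrolment target agree.

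**Predictability of a full stack.** Inputs: 5 A and 5 B per stack (Treatment allocation). Assumptions: one stack per severity group, used to the end, and a guesser who knows the earlier draws and always names the arm with more envelopes left.

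- Expected correct guesses for n of each arm: n + (4^n / C(2n, n) − 1)/2. With n = 5: 5 + (1024/252 − 1)/2 = 5 + 1.532 = 6.532 of 10, or 65.3%. Over three stacks: 3 × 6.532 = 19.6 of 30, against 15 by chance.
- Draws known with certainty (one arm exhausted): 2n/(n + 1) = 10/6 = 1.667 per stack, or 5.0 of 30.

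| Draw | Chance of a correct guess | Chance the draw is certain |
|---|---|---|
| 1 | 0.500 | 0 |
| 2, 3 | 0.556 each | 0 |
| 4, 5 | 0.595 each | 0 |
| 6 | 0.643 | 0.008 |
| 7 | 0.643 | 0.048 |
| 8 | 0.722 | 0.167 |
| 9 | 0.722 | 0.444 |
| 10 | 1 | 1 |

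The columns sum to 6.53 and 1.67, which confirms the formulas.

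**Uneven filling.** The documents give no severity mix, so I assumed two: 30 people arriving, with at most 10 drawn per stack.

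| Assumed mix | Mean draws made | Correct guesses | Certain draws |
|---|---|---|---|
| One third each | 26.9 | 63.3% | 3.2 |
| 20/50/30% | 24.3 | 62.6% | 2.7 |

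The count of certain draws is sensitive to filling; the share guessed correctly hardly moves. Whether the two sites share stacks is not stated, and separate stacks would change these figures.

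**COPM bias.** Let d1 and d2 be the between-group shifts in COPM score that come from the interviewer knowing the group at O1 and at O2, and let b be the regression slope of posttest 1 on pretest.

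- Bias of the posttest 1 regression: d2 − b × d1.
- Bias of the between-group difference in change from O1 to O2: d2 − d1.

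The documents give none of d1, d2 or b. Because the same unblinded person gives the COPM at both times, d2 cannot be set to zero. Shifts in the same direction partly or wholly cancel; shifts in opposite directions add. Neither the size nor the sign of the net bias can be obtained.

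**The case against.** **The timing is not certain.** In Table 1, M and R stand beside the group labels rather than under a week, so the table is weak evidence of order. No text says that O1 is a later visit than screening, and Figure 2 is not shown. This stands as a limit on confidence. The statement that assignment takes place at screening still makes assignment before O1 the most natural reading, and no available text puts O1 first.

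**Removing the baseline shift alone might not reduce the net COPM bias.** If the interviewer's knowledge moves O1 and O2 scores the same way, the two shifts now partly cancel, and removing d1 leaves d2 exposed. This stands. A reader might infer that the posttest 1 comparison is biased by a definite fraction of an SD, or that the fix leaves a definite percentage of the bias. The documents support neither: any such figure would need knowledge of the group to distort O1 but not O2 or O3.

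**The fix leaves the tally in place.** This also stands. A reader might infer that the 65.3% is what the change removes. It is not: while the 5/5 composition is known, the investigator can still guess before writing down eligibility or severity. The written record prevents changes after opening, and the independent holder prevents envelopes being opened early or reordered.

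**The scope is narrow.** The COPM is self-rated and guides treatment, WMFT and MAL are given by blinded evaluators, and the study is described as pilot work. The first two points confine the baseline concern to the COPM. Self-rating does not remove the influence of an interviewer who knows the group, and pilot status does not help when the pilot is meant to yield effect sizes.

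**Conclusion.** The concern holds as a design weakness that is cheap to correct. One role screens, scores severity, assigns, treats most participants and gives one of the three primary-endpoint measures. On the most natural reading, every baseline COPM is taken with the group known.

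Predictability is 65.3% correct guesses and 5.0 of 30 certain assignments if one stack per severity group fills to 10, with about 2.7 to 3.2 certain under the assumed uneven mixes. These figures assume that earlier draws are tallied; they measure opportunity and are not evidence that anyone would steer enrolment.

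No size or direction can be put on COPM bias. The baseline concern does not extend to WMFT or MAL, and the posttest 2 regression does not use the pretest. Confidence is high on the roles and the stack composition, and lower on the order of assignment and O1.

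**What to change.** In Treatment allocation and Table 1, place R after O1. Suggested text:

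> Eligibility and severity group are recorded in writing at screening. All O1 assessments, including the COPM, are then completed. Sequentially numbered opaque envelopes for each severity group are prepared and held by a person who does not screen, treat or assess. This person confirms that the records and the O1 assessments are complete before opening the next envelope for that severity group and reporting the assignment. Upcoming assignments are not disclosed to the primary investigator.

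Existing personnel can hold the envelopes. The academic advisor is one option but is not fully independent, being the founder of the approach, the supervisor of treatment plans and the checker of data analyses.

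Keep the stratification and the 5/5 balance. Shorter fixed blocks of known size would be more predictable: 2.833/4 = 70.8% correct for blocks of 4 and 1.5/2 = 75% for blocks of 2. State whether the two sites share stacks. Reconcile the Data monitor section with the Study plan and Treatment Fidelity sections on who gives the COPM, and check Figure 2 against the new order.

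**Cost.** One paragraph, one change in Table 1, and one contact with the holder per participant at both sites. Sample size, strata and balance do not change. Orthosis fabrication and fitting would have to follow O1; no fabrication time is given, so Group A may need an added visit.

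**What it achieves.** The baseline COPM is taken without certain knowledge of the group for most participants: with full stacks, on average 5.0 of 30 would still be certain from the tally, instead of all 30 being known. It does not stop guessing at screening, and it does not blind the COPM at O2 or O3.

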### **Sample size estimation**

We plan to enroll 30 participants in the study. Based on anticipated number of screen failures and/or withdrawals, the maximum number of participants whom we will consent in order to achieve the scientific objectives of this study is 40. Note that the number of participants described above is a rough estimate of the sample size needed, since there is no evidence to address the primary question of interest. This proposed project involves pilot/preliminary investigation, which will be used to calculate the effect sizes that need to be used for the future study.

### **Participant selection**

The target population for this study is stroke patients who have a hemiparetic arm. Subjects will be recruited from a) local hospitals and institutions in the Twin Cities metro area, including advertising at Fairview hospitals and the stroke center at the North Memorial Hospital and b) the Onsite clinic at the University of Puget Sound at which the PI was a graduate from the occupational therapy program.

Inclusive criteria in this study include:

#### Participants

- 1) Have a diagnosis of stroke for at least three months,
- 2) Be 18 years of age or older,
- 3) Have sufficient cognitive function to follow three-step verbal instruction and provide independent consent,
- 4) Have appropriate trunk and lower extremity function that does not interfere with performance of the upper extremity,
- 5) Have at least minimum voluntary movement in the upper extremity (10

degrees of shoulder flex/abduction, 10 degrees of elbow flexion/extension), and

6) Not receive any rehabilitative interventions concurrent with the study.

Exclusive criteria include:

- 1) Severe joint deformities or contractures of the affected upper extremity that limit range of motion required for functional tasks,
- 2) Capability of voluntarily extending the wrist and fingers through the full range,
- 3) Have serious uncontrolled medical problems, such as seizures and visual impairment.

Interested persons, who begin pharmacological treatments for management of spasticity, such as Botox and Baclofen, before the study and sustain these throughout the study period, will be permitted to participate. Interested persons who use pharmacological treatment for spasticity reduction, such as Botox or Baclofen, and then stop treatment, are excluded until they are at least 4 months past their last use of the medications. Persons who enroll in the study while using Botox or Baclofen will be **removed** from the study if they stop that treatment during the study period. Timeline for consenting is illustrated in Figure 2.

[figure not shown]

Figure 2. Timeline for consenting.

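### Randomised participants who stop Botox or Baclofen are removed from the study, so later assessments are lost for a post-randomisation reason that could differ between groups

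*Combined protocol and SAP*

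**What the plan says.** The combined protocol and SAP admits users of antispasticity drugs on a condition. Under Participant selection, those who start such a drug "before the study and sustain these throughout the study period, will be permitted to participate". Those who enrol on Botox or Baclofen are removed "from the study if they stop that treatment during the study period". The wording is removal from the study, not only from the intervention.

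Under Treatment allocation, the primary investigator "will randomly assign eligible participants at the screening session using sealed envelopes". Within each of three severity classes participants are "randomized in a 1:1 allocation ratio to either the Group A or B", with "10 for each matched group with 5 Group As and 5 Group Bs".

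Under Sample size estimation: "We plan to enroll 30 participants in the study". The consent limit of 40 is explained by screen failures and withdrawals together. No separate figure is given for removals under the drug rule.

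Data analysis names three methods:

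- a linear mixed-effects model with group, time and their interaction, and participant as a random effect;
- general linear models at posttest 1 (pretest as covariate) and at posttest 2 (posttest 1 as covariate);
- paired t tests within each group.

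The documents do not define an analysis set, assessment after removal, a method for missing data, or reporting of removals by group.

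**The concern.** The rule acts on people who already have an allocation, and it is triggered by something that happens afterwards. Group A wears an orthosis in weeks 2 to 7 while Group B has no treatment, and participants know whether they wear it. The protocol hopes to prevent or reduce secondary complications, and it lists muscle soreness and restricted movement as possible risks of the orthosis. Either could bear on whether someone continues a spasticity drug, so stopping could differ in frequency, or in the kind of person who stops, between the groups.

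If it does, the people compared at later visits are no longer the groups that were randomised, and the contrast can be biased in either direction. The trial is small: with 5 per arm in each severity class, one removal takes 1/5 = 20% of a cell. The results are meant to supply effect sizes for a future study, so a bias here would carry into that study's sample size.

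**Working it through.** **The plan's own figures.** 3 severity classes × 10 = 30, that is 15 per arm, as stated. The consent limit of 40 corresponds to 30/(1 − 0.25) = 40, an implied combined loss of 25%. That percentage is back-calculated and is not in the plan. No alpha, power, effect size or SD is given, and the plan itself says "the number of participants described above is a rough estimate of the sample size needed", so there is no power calculation to reproduce.

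**What is lost, by time of stopping.** Assessments are O1 (week 1), O2 (week 8) and O3 (week 15). Assuming that data already collected are kept:

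| Stop occurs | Visits held | Posttest 1 linear model | Posttest 2 linear model | Paired t tests | Mixed model |
|---|---|---|---|---|---|
| After O1, before O2 | O1 | lost | lost | both periods lost | uses O1 |
| After O2, before O3 | O1, O2 | kept | lost | second period lost | uses O1, O2 |

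The mixed model's use of partial records is valid only if the missing values are missing at random given the observed data.

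**Size.** The number of drug users, the number who stop and how their outcomes differ are not in the documents. What follows is therefore assumed: no true effect, k of 15 removed from one arm and none from the other, and all removed people lying δ SD from their full arm's mean in the same direction.

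- Shift in the arm mean = kδ/(15 − k).
- Standard error of the difference = √(1/(15 − k) + 1/15) SD.
- The false-positive rate is the rejection probability of a two-sided 5% t test, from the noncentral t with 28 − k degrees of freedom and noncentrality shift/SE.

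| k | SE (SD) | Shift, δ = 0.5 | False positive | Shift, δ = 1 | False positive |
|---|---|---|---|---|---|
| 1 | 0.372 | 0.5/14 = 0.04 | 5.1% | 1/14 = 0.07 | 5.4% |
| 2 | 0.379 | 1/13 = 0.08 | 5.4% | 2/13 = 0.15 | 6.8% |
| 3 | 0.387 | 1.5/12 = 0.13 | 6.1% | 3/12 = 0.25 | 9.5% |

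With nobody removed the SE is √(2/15) = 0.365 SD. Losing 3 from one arm raises it by a factor of 0.387/0.365 = 1.06.

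**Second convention.** If the gap g is measured from the people who remain, the shift is kg/15. For k = 1 to 3 this gives 0.03 to 0.10 SD at g = 0.5 and 0.07 to 0.20 SD at g = 1.

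**Removals in both arms.** The bias is then −g(f_A − f_B), where f is the share of each arm removed. Assume drug users make up 20% to 40% of each arm and stop at 25% in A versus 0% in B, or 50% versus 10%. The smallest case is 0.5 × (0.20 × 0.25) = 0.025 SD. The largest is 1 × (0.40 × 0.50 − 0.40 × 0.10) = 0.16 SD. With the same stopping rate and the same gap in both arms, f_A − f_B = 0 and the bias is 0.

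**With adjustment for pretest** (assumed correlation 0.7, residual SD √(1 − 0.49) = 0.71). If removed people do not differ at pretest, the whole 1 SD gap remains and the rates are 5.8%, 8.5% and 14.0%. If they differ by 1 SD at pretest as well, the remaining gap is 1 − 0.7 = 0.3 SD and the rates are 5.1%, 5.3% and 5.8%.

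**The case against.** Holding background medication constant is an understandable aim, and admitting users only if they sustain treatment should make stopping uncommon. Sample size estimation foresees withdrawals. The trial is a pilot, and every shift computed above is below one standard error. All of that stands and limits the weight of the point. However, the consent allowance does not say that randomised participants are replaced, and replacement would not restore the people selectively lost.

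Three stronger readings are tempting, and the documents do not support them.

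- *That the O2 and O3 data of everyone who stops are lost.* Nothing orders deletion of data already collected. A person who stops after week 8 already has O2, and the mixed model can use partial records. What is certain is only that visits due after removal are not made.
- *That the orthosis causes people to stop their drug.* This is conjecture. The device is designed to assist forearm rotation, the background section associates recovery with active movement and strength rather than spasticity, and no spasticity measure is among the outcomes. A difference between groups is possible but not shown.
- *That the false-positive rate rises to 14%.* That needs three removals, all from one arm, all in one direction, a 1 SD gap at the post-test and no gap at pretest. It is the extreme of the range.

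**Conclusion.** The point holds as a design weakness written into the plan: a stated post-randomisation exclusion, with nothing elsewhere to offset it. It is not a demonstrated bias. Its size depends on how many people stop, in which group, and how their outcomes differ, none of which is known. In the unadjusted one-arm, same-direction scenarios the shift is 0.04 to 0.25 SD and the false-positive rate 5.1% to 9.5%. One removal barely matters, and equal stopping with equal gaps gives no bias. The change is worth making because it is cheap and because a visit not made cannot be recovered at the analysis stage.

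**What to change.** In Participant selection, replace removal from the study with continued assessment: anyone who stops Botox or Baclofen and still consents attends the scheduled O2 and O3, the stop and its date are recorded, and all data are kept. In Data analysis, state that the main analysis includes everyone in the group to which they were randomised, that stops are reported by group, and that the analysis without those who stopped is given as a sensitivity analysis.

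This concerns follow-up and analysis only. It takes no position on whether the drug, the orthosis or the task-oriented therapy continues after a stop.

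The cost is a short edit to each of the two sections and at most two visits per person, both already in the schedule. The small downside is that some outcomes are measured under changed medication, which the sensitivity analysis addresses.
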